2 OBJECTIVES AND ENDPOINTS

Primary Objective	Primary Endpoints
To evaluate the ocular safety of a single dose of AG-920 after topical ocular administration of Articaine Sterile Topical Ophthalmic Solution (2 drops 30 seconds apart)	Visual acuity, intraocular pressure, biomicroscopy, AEs, TEAEs, SAEs, withdrawals due to TEAEs
Secondary Objectives	Secondary Endpoints
A subset of up to 20 subjects (with expectations that 12 receiving AG-920 and 6 receiving vehicle) will undergo specular microscopy prior to and 3 months after receiving masked study medication to evaluate the effect of AG-920 on corneal endothelial cell count (ECC).	Mean change from baseline in corneal endothelial cell density after treatment with AG-920

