6.5 Follow-Up Phone Call (Day 2-5)

Subjects will receive a phone call from site staff between Days 2-5, which is 1-4 days (24-96 hours post-dose) following treatment with IMP. Subjects will be asked about

- Assess for AEs
- Collect any changes to concomitant medications
- If they are in the specular microscopy group, they will be reminded of their visit at Day 90 (Visit 3) and appointment confirmed.

If there are any ongoing adverse events, the subject will be instructed to return to the investigator's office for appropriate evaluation. If there are no ongoing adverse events, the subject will be considered completed.

For subjects NOT in the specular microscopy subset, subjects will be thanked for their participation and released to follow their normal standard of care.

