8.3 Adverse events¹

All AEs occurring after the first dose of IMP and throughout the remainder of the study period (Follow-up Phone Call; Visit 3 for subjects participating in specular microscopy) will be considered TEAEs and must be documented on the relevant Electronic Data Capture (EDC) pages and in the source documents. Whenever possible, the diagnosis, if available, and not the symptoms should be reported as the AE. AEs and Serious Adverse Events (SAEs) will be coded according to the Medical Dictionary for Regulatory Activities (MedDRA).

Documentation of adverse events/adverse reactions includes start date and stop date, severity, action(s) taken, seriousness and outcome.

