9.4.8 Adverse Events

Verbatim descriptions of AEs will be mapped to MedDRA thesaurus terms and be presented in a data listing. Treatment emergent AEs, those that occur after the first dose of study medication, will be summarized by treatment group using frequency counts and percentages for each system organ class (SOC) and preferred term (PT) within each SOC. Summaries will be presented separately for ocular and non-ocular AEs. These summaries will also be presented by the relationship to the Investigational Medical Product (related, unrelated) and by severity of the AE (mild, moderate, severe). Fisher's exact test will be used to test the difference in proportions of subjects with each AE between treatment groups (SOC and PT).

9.5 *Procedure for accounting for missing, unused, or spurious data*

For this safety study, only observed data will be used. This is no planned method for imputation of missing data.

9.6 *Procedure for reporting deviations from the statistical plan*

Any deviations from the statistical plan will be described and a justification given in the final statistical report.

9.7 *Data listings*

Data listings will be prepared for all data on the database.

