2.2 Description of Trial Design

This is a Phase 3, randomized, placebo-controlled, double-masked, parallel-group design study of AG-920 topically administered versus placebo (vehicle) in healthy subjects. The study will evaluate the safety following one dose of [REDACTED] Sterile Topical Ophthalmic Solution (AG-920) in reference to placebo. Eligible subjects will be randomized in a 2:1 ratio to receive a single dose of AG-920 or matching placebo into one eye, designated as subject's study eye. The application of one single dose of AG-920 consists of 2 drops 30 seconds apart into the subject's study eye.

The study consists of two visits and a follow-up phone call: one screening visit on Day -2 to Day 0 (Visit 1), one baseline/assessment visit on Day 1 (Visit 2), and one follow-up phone assessment on Day 2-5 (Phone Follow-Up). In addition, approximately 18 subjects from one site will be asked to return to the clinic for an additional visit (Visit 3) 90 days following Visit 2 to undergo specular microscopy and other safety evaluations.

Following the screening visit, eligible subjects will be randomly assigned a study eye (right eye=OD or left eye=OS) and study medication (active or placebo). Following dose administration, adverse events will be monitored. Safety assessments of BCVA, IOP, biomicroscopy, and external eye exam, will be performed on both eyes 60 to 90 minutes post dosing.

All subjects who are randomized and who receive the study medication on Day 1 will be followed up with a phone call to on Day 2-5 for safety assessment. A subset of subjects will return to the clinic for Visit 3, which is 90 days following Visit 2, for specular microscopy with all of the safety assessments.

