2.9.3 Safety analysis

Treatment Exposure

Frequencies of exposure to the study medication will be calculated based on the number of drops the subject has received over the course of the study. Frequencies of exposure will be categorized as the following: 1 drop and 2 drops. Frequencies of exposure will be summarized by treatment for the safety population defined in Section 3.1, as well as by gender.

Compliance rates will be calculated by dividing the number of drops received by the number of drops that should have been given during the application of dose. Compliance rates will be summarized.

Early Termination

Subject disposition will be summarized by treatment and will be listed for those subjects who are terminated early. This listing will include demographic variables, treatment assigned, number of drops received, termination date, and the primary reason for early termination.

Adverse Events

Adverse events will be coded for preferred terminologies using Medical Dictionary for Regulatory Activities (MedDRA). AEs will be grouped into pre-treatment AE, treatment-emergent AE, and post-treatment AE and will be reported separately, based upon the start date and time of the events and the start date and time of the treatment.

Adverse events will be defined as pre-treatment AEs if they occur prior to the treatment start date and time; as treatment-emergent AEs if they occur on or after the treatment start date and time and before the next day; and as post-treatment AEs if they occur after the treatment date.

Frequency of treatment-emergent AEs will be calculated for each body system, by preferred terminology, by treatment group, for number of subjects and percentage reporting the event. The severity of the adverse events and the relationship to the investigational product will be summarized for each body system and preferred terminology by treatment group. Withdrawals due to adverse events will be summarized for each body system and preferred terminology by treatment group and will be listed with demographic variables for individual subjects.

Serious adverse events (SAE) (including deaths) will be listed for individual events.

Narratives will be provided for all deaths, non-fatal serious adverse events, and subjects withdrawn due to adverse events.

Best Corrected Visual Acuity (BCVA)

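### The SAP ends treatment-emergent AEs at midnight on the dosing day, while the protocol counts them to the follow-up call or Visit 3, so a named primary endpoint has two definitions.

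*SAP*

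**What the plan says.** Protocol 2 lists among the primary endpoints "AEs, TEAEs, SAEs, withdrawals due to TEAEs". The protocol defines a TEAE twice, consistently:

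- Protocol 8.3 counts AEs after the first dose through the rest of the study period, which it specifies as "Follow-up Phone Call; Visit 3 for subjects participating in specular microscopy".
- Protocol 9.4.8 states: "Treatment emergent AEs, those that occur after the first dose of study medication, will be summarized by treatment group". It gives no upper time limit.

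Protocol 6.5 places the call on Days 2-5, "which is 1-4 days (24-96 hours post-dose) following treatment with IMP". Protocol 3.6.1 and 6.6 place Visit 3 at 90 ± 5 days. The SAP keeps this follow-up; SAP 2.2 says: "All subjects who are randomized and who receive the study medication on Day 1 will be followed up with a phone call".

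SAP 2.9.3 defines the classes differently. It classes events "as treatment-emergent AEs if they occur on or after the treatment start date and time and before the next day", and later ones "as post-treatment AEs if they occur after the treatment date". The classes are reported separately.

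SAP 5.3 then tabulates TEAEs by whether onset was on or off the treatment day (Tables 4.3.1-4.3.3). It limits the severity/relationship table (4.4.1) and the discontinuation table (4.4.2) to TEAEs. SAP 2.9.3 sets no such limit on those summaries: "The severity of the adverse events and the relationship to the investigational product will be summarized", and it treats withdrawals due to adverse events in the same way.

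**The concern.** An AE that starts on Day 2 is a TEAE under the protocol and a post-treatment AE under SAP 2.9.3. Both texts cannot be followed. This is a safety-only study, and the quantity with two definitions is a named primary endpoint, so two programmers could report different TEAE rates from one dataset. Under the SAP window the rate is too low by the protocol's definition in any arm with a late onset.

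The call takes place at least 24 hours after dosing, so much of the period it covers lies outside the SAP's TEAE class. Events that start in that period would have no by-eye table and no SAE incidence table. Under 5.3 they would also have no severity/relationship table and no discontinuation table. If the conflict is found only after unmasking, the choice of definition would be made with results in view.

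**Working it through.** The plan states no figure to reproduce. The check is a comparison of texts, followed by arithmetic on scale.

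**1. Classification of an AE by onset**

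| Onset | Protocol 8.3 / 9.4.8 | SAP 2.9.3 | SAP 5.3, Tables 4.3.1-4.3.3 |
|---|---|---|---|
| Dosing day, after dosing | TEAE | TEAE | TEAE, on-treatment day |
| Day 2 to the call | TEAE | Post-treatment AE | TEAE, off-treatment day |
| After the call to Visit 3 (subset) | TEAE | Post-treatment AE | TEAE, off-treatment day |

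Under 2.9.3 the off-treatment-day category is always empty, so 5.3 and 2.9.3 cannot both be right. All three texts classify by onset, so an event that began on the dosing day but was first reported at the call is a TEAE throughout.

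**2. Tables that depend on the definition (SAP 5.3)**

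4.2.2, 4.2.3, 4.2.5, 4.2.6 (4) + 4.3.1-4.3.3 (3) + 4.4.1-4.4.7 (7) = 14.

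Among the preferred-term incidence tables, late events would appear only in Table 4.2.4. That table is in the SAP 7 list but is not described in 5.3.

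**3. Window length**

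Dosing clock time is not given; 08:00 to 16:00 is assumed.

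- SAP window: 24:00 − 08:00 = 16 h; 24:00 − 16:00 = 8 h.
- Protocol window to the call: 24 to 96 h. The SAP window covers at most 16/24 = 67% and at least 8/96 = 8%.
- Subset, to Visit 3 (85-95 days): at most 16/(85 × 24) = 0.8%.

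These are shares of time, not of events.

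**4. Subjects relabelled**

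Let p be the proportion of the 240 subjects with an AE starting on Day 2 or later (assumed). Expected number = 240p; chance of at least one = 1 − (1 − p)^240.

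| p | Expected subjects | Chance of at least one |
|---|---|---|
| 0.2% | 0.48 | 38% |
| 1% | 2.4 | 91% |
| 5% | 12 | >99.9% |

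**5. One preferred term on AG-920 (n = 160, assumed counts)**

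Rate under the SAP = (cases − late cases)/160, with late cases rounded to whole subjects.

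| Cases | 0% late | 20% late | 40% late |
|---|---|---|---|
| 10 | 10/160 = 6.25% | 8/160 = 5.0% | 6/160 = 3.75% |
| 16 | 16/160 = 10.0% | 13/160 = 8.1% | 10/160 = 6.25% |
| 24 | 24/160 = 15.0% | 19/160 = 11.9% | 14/160 = 8.75% |

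Table 4.2.3 needs more than 5% in either arm. On AG-920, 9/160 = 5.6% qualifies and 8/160 = 5.0% does not. The AG-920 rate therefore fails the rule only if at least 10 − 8 = 2, 16 − 8 = 8 or 24 − 8 = 16 cases are late. The term still enters the table if placebo has at least 5/80 = 6.25% on the dosing day (4/80 = 5.0% does not qualify).

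**The case against.** The strongest reply is that the practical effect is modest and the wording partly points to the protocol's reading anyway.

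- **Late events are still reported.** This stands. They reach Table 4.2.4, the AE and SAE listings, the narratives, the disposition tables 1.4.1-1.4.2 if the subject discontinues, and probably the overall summaries 4.1.1-4.1.2. AEs and SAEs are primary endpoints in their own right and do not depend on the TEAE window.
- **Read alone, 2.9.3 does not remove late events from the severity, relationship and withdrawal summaries.** This is correct. They drop out of Tables 4.4.1 and 4.4.2 only when the 2.9.3 window is combined with the table wording in 5.3. That is a further inconsistency to resolve.
- **The on/off-treatment-day split shows that the longer window was intended.** It may have been, but a separate post-treatment table (4.2.4) points the other way. The table shells are not in the reviewed text, so which rule would be programmed cannot be seen.
- **Late events should be few.** This is plausible: Protocol 1.2 expects mainly temporary effects upon instillation. Late withdrawals should be rarer still after a single dose. The rates, case counts and clock times above are all assumed, and the shares of window length overstate the likely share of events.
- **No bias between arms is shown.** This is agreed, and none is claimed.

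These points limit the size of the problem. They do not leave the endpoint with one definition.

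**Conclusion.** The concern holds. SAP 2.9.3 conflicts with Protocol 8.3 and 9.4.8 and with SAP 5.3 on what a TEAE is, and TEAEs are a named primary endpoint. It should be corrected before unmasking. Confidence in the conflict of wording is high, because it rests on the text alone.

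The effect on reported rates cannot be calculated, since the documents give no AE rates or onset times. Under the assumed late-onset rates of 0.2% to 5%, roughly 0.5 to 12 of 240 subjects would be relabelled. Entry to the more-than-5% table is sensitive only for terms close to the cut-off. Withdrawals due to TEAEs are less exposed, because 2.9.3 also promises an unrestricted withdrawal summary and the disposition tables give termination reasons whatever the AE onset. Rates for AEs of any onset are unaffected.

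**What to change.** Before unmasking, amend the SAP as follows:

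1. In 2.9.3, adopt the window of Protocol 8.3: onset after the start of dosing through the follow-up call, or through Visit 3 for the specular microscopy subset. State that a subject who received only one drop is included, to match the safety population in SAP 3.1. This needs saying because the protocol counts from the first dose, and Protocol 9.3 takes a dose as two drops.
2. Use this definition in all 14 TEAE tables, with on/off-treatment day as the sub-split in Tables 4.3.1-4.3.3.
3. Keep Table 4.2.4, if wanted, as a subset of TEAEs and not as a class that excludes them. Describe it in 5.3.
4. Count subset events after the call in the TEAE total and also show them in a flagged row. The rate from dosing to the call can then be read for all subjects on a common window.
5. Make 2.9.3 and 5.3 agree on which AEs enter the severity, relationship and withdrawal summaries.

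The cost is SAP wording, one changed flag in the AE dataset, a rerun of the 14 tables, and one extra row for about 18 subset subjects. Table 4.2.4 needs relabelling, and Tables 4.1.1-4.1.2 need a rerun if they carry a TEAE count. Reported TEAE rates may be somewhat higher. No new data or subjects are needed.

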1.1 Findings from nonclinical and clinical studies

1.2 Potential Risks and benefits to human subjects

Minimal risks are expected with AG-920. Based upon clinical trials conducted to date, expected risks for subjects may include temporary, mild conjunctival/ocular hyperemia, eye pain, instillation site reaction (stinging/burning), and conjunctival hemorrhage. upon instillation of the investigational medicinal product (IMP). For any additional information on AG-920 use, please refer to the [Investigator's Brochure](#).

As this study is to be conducted in healthy subjects, there is no anticipated benefit other than the possibility that a subject's participation in the present study may help others in the future to have more options for local anesthesia before ophthalmic procedures.

Any new, unexpected adverse events (AEs) present among subjects in this clinical trial will be communicated to Investigators and to ethics committees or Institutional Review Board (IRBs) in accordance with local regulations.

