9.4 Statistical methods to be employed

9.4.1 General Considerations

All continuous study assessments will be summarized by treatment and time point (as applicable) using descriptive statistics (n, mean, median, standard deviation, minimum, and maximum). All categorical study assessments will be summarized by treatment and time point (as applicable) using frequency counts and percentages.

All study data will be listed by treatment, subject, time point, and eye (as applicable).

Statistical methods will be more fully described in a separate document (Statistical Analysis Plan).

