9.4.7 Analysis of Safety

Intraocular pressure, slit lamp biomicroscopy, external eye exam, intraocular pressure and cardiovascular measures will be summarized at each measured time point using discrete summary statistics.

Visual Acuity data will be summarized at each time point using both continuous summaries (Logarithmic Minimum Angle of Resolution, logMAR), including change from baseline, and discrete summaries, including change from baseline in the number of lines and the proportion of subjects with a worsening of ≥ 3 lines from baseline.

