2.8 Handling of Missing, Incomplete, and Repeat Data

There are no efficacy parameters in this study.

For safety parameters, missing or invalid data will be treated as missing for the corresponding assessment of a visit.

All data records are identified by study visit and/or assessment time point. Should repeated data records exist within a study visit and/or assessment time point, the first valid data record will be utilized for any statistical analyses of the corresponding study visit and/or assessment time point. All existing data records including the repeat data records in the study database will be presented in data listings and CRF data tabulations.

Any resultant incomplete or missing data of safety parameters will be treated as missing in the statistical analyses involving these parameters.

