BCVA will be summarized in logMAR units by treatment for the screening (pre-dose) and Day 1 (post-dose), using number of observations, mean, standard deviation, minimum, median, and maximum values. The analysis will be based on the safety population defined in [Section 3.1](#).

For both study eye and fellow eye, changes in BCVA at post-dose from screening (pre-dose) will be analyzed for differences between AG-920 and placebo groups, using analysis of covariance (ANCOVA), with the pre-dose measurement as the covariate. Any BCVA changes of >3 lines from baseline will be flagged.

Intraocular Pressure (IOP)

Mean or median IOP values observed at a time point will be summarized in mmHg units by treatment for the screening (pre-dose) and Day 1 (post-dose), using number of observations, mean, standard deviation, minimum, median, and maximum values. The analysis will be based on the safety population defined in Section 3.1. Subjects who participated in the specular microscopy subset will also have IOP measured at Visit 3.

IOP measurements can be performed using a Tonopen® or Goldmann Tonometer. If a Goldmann tonometer is used, then two consecutive IOP measurements of each eye will be obtained. If the two measurements differ by more than 2 mm Hg, a third measurement should be obtained. IOP will be analyzed as the mean of two measurements or as the median of three measurements.

For both study eye and fellow eye, changes in IOP at post-dose from screening (pre-dose) will be analyzed for differences between AG-920 and placebo groups, using analysis of covariance (ANCOVA), with the pre-dose measurement as the covariate.

Biomicroscopy (Slit Lamp)

Total severity scores of biomicroscopy (slit lamp of seven items on grading scale, including lid erythema, lid edema, conjunctiva hyperemia, conjunctiva edema, corneal edema, anterior chamber cells, and anterior chamber flare) will be summarized and analyzed individually by treatment for the screening (pre-dose) and Day 1 (post-dose), and Visit 3 (for specular microscopy subjects) using number of observations, mean, standard deviation, minimum, median, and maximum values. The analysis will be based on the safety population defined in [Section 3.1](#).

For both study eye and fellow eye, changes in the total severity score at post-dose from screening (pre-dose) will be analyzed for differences between AG-920 and placebo groups, using analysis of covariance (ANCOVA), with the pre-dose measurement as the covariate.

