5.5 Intraocular Pressure

Descriptive and inferential statistics of IOP will be presented by treatment for the pre-dose (screening) and post-dose assessments and changes in post-dose assessment from pre-dose in Table 5.2.1 for the study eye and in Table 5.2.2 for the fellow eye.

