5.6 Biomicroscopy and External Eye Exam

Descriptive and inferential statistics of biomicroscopy (Slit-Lamp) total severity score will be presented by treatment for the pre-dose (screening) and post-dose assessments and their changes in post-dose assessment from pre-dose in Table 6.1.1 for the study eye and in Table 6.1.2 for the fellow eye.

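### Slit lamp, a primary endpoint, is given only continuous statistics and a total-score ANCOVA in the SAP where protocol 9.4.7 asks for discrete summaries; as a lesser point, heart rate and blood pressure have no summary table

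*SAP*

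**What the plan says.** Protocol section 2 lists biomicroscopy among the primary endpoints. Protocol 9.4.7 states that "slit lamp biomicroscopy, external eye exam, intraocular pressure and cardiovascular measures will be summarized at each measured time point using discrete summary statistics". The next paragraph of 9.4.7, on visual acuity, contrasts continuous with discrete summaries and puts a proportion of subjects under the discrete ones. So discrete there reads as counts and percentages, which is also what protocol 9.4.1 prescribes for categorical assessments.

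SAP 2.9.3 describes the slit lamp as seven graded items: lid erythema, lid edema, conjunctival hyperemia, conjunctival edema, corneal edema, anterior chamber cells and anterior chamber flare. Total severity scores over these "will be summarized and analyzed individually by treatment for the screening (pre-dose) and Day 1 (post-dose"), with the six continuous statistics. Then "changes in the total severity score at post-dose from screening (pre-dose) will be analyzed for differences between AG-920 and placebo groups", using ANCOVA with the pre-dose value as covariate. SAP 5.6 adds: "Descriptive and inferential statistics of biomicroscopy (Slit-Lamp) total severity score will be presented by treatment". Tables 6.1.1 and 6.1.2 are titled as severity scores for the study and fellow eye.

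Heart rate and blood pressure are safety measures in protocol 8.1 and SAP 2.6. They are not primary endpoints.

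**The concern.** A graded clinical sign is an ordered category, and the protocol asks for it to be reported as one. The SAP treats it as a continuous score and, in 5.6, adds seven signs into one number. For visual acuity, SAP 5.4 carries over both kinds of summary from the protocol. For slit lamp it carries over only the continuous kind and gives no reason.

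This matters because the signs differ in meaning. Protocol 1.2 says that "expected risks for subjects may include temporary, mild conjunctival/ocular hyperemia", so some surface redness is anticipated. Anterior chamber cells are not among the risks named there. A total score gives a point of one the same weight as a point of the other. The trial was sized for safety exposure, so its main product is a clear account of how many subjects showed which finding.

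**Working it through.** **Inputs.** Arm sizes are 160 and 80 (SAP 2.5). They agree with the 2:1 ratio: 240 × 2/3 = 160 and 240 × 1/3 = 80. The documents give no power or precision figure to reproduce. The grading scale is not in the text available for review, so I assume integer grades that can rise by 2. All subject counts below are illustrative.

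**1. What the total score hides.** In AG-920 (n = 160), 5 subjects gain 2 points in total and 155 do not change. Pre-dose grades are the same in both cases, and the 5 subjects start at grade 0 on the items concerned.
- Case A: each gains 2 grades of anterior chamber cells.
- Case B: each gains 1 grade of lid erythema and 1 of conjunctival hyperemia.

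Change in total score, in both cases:
- mean = (5 × 2)/160 = 0.0625
- SD = √[(5 × 2² − 160 × 0.0625²)/159] = √(19.375/159) = 0.349
- minimum 0, median 0, maximum 2

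Every subject has the same arm, pre-dose total and change in A as in B, so the ANCOVA estimate, standard error and p-value are also identical. A table by item and grade separates the cases: grade 2 anterior chamber cells rise by 5/160 (3.1%) in A and by 0/160 in B.

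**2. Not a question of significance.** For 5/160 against 0/80, the two-sided Fisher p-value is 0.17. What is gained is sight of the affected sign.

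**3. If the items are summarized one by one.** The word *individually* in SAP 2.9.3 may mean item by item. Then A and B are told apart by sign, and what is missing is the count by grade. In the simplest case (an item at 0 in everyone pre-dose, on a 0 to 2 scale) the counts could be back-calculated from n, mean and SD, but they would not be displayed.

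**4. Support for an optional worsening count only.** Take one item with 9/160 at grade 1 pre-dose.

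| Pre→post | 0→0 | 0→1 | 0→2 | 1→0 | 1→1 | 1→2 | Worse |
|---|---|---|---|---|---|---|---|
| X | 141 | 9 | 1 | 5 | 0 | 4 | 14 (8.8%) |
| Y | 145 | 1 | 5 | 1 | 8 | 0 | 6 (3.8%) |

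Both have pre-dose counts 151/9 (grades 0/1), post-dose counts 146/9/5 (grades 0/1/2), change summing to 10 and squared change summing to 22. Hence mean change is 0.0625 and SD = √[(22 − 0.625)/159] = 0.367 in both. One subject worsens by 2 grades in X and five do in Y. Counts by grade at each time point agree as well, so meeting 9.4.7 would not separate X from Y. Only a count of subjects worsening from pre-dose does.

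**5. Heart rate and blood pressure.** SAP 2.9.3 has no paragraph on them and SAP 5.1 to 5.8 no section. The table list in SAP 7 has no table, and Listings 1 to 10 (SAP 8) and Data 1.1 to 8.1 (SAP 10) have no entry. Protocol 9.4.7 asks for a summary of cardiovascular measures at each measured time point.

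**The case against.** **Adverse events already name the sign.** This is the strongest objection, and most of it stands. Protocol 8.3.1 counts any abnormal sign as an adverse event to be documented, whether or not related. The post-dose slit lamp is done 60 to 90 minutes after dosing (SAP 2.2), inside the SAP's same-day treatment-emergent window. Such events are counted by preferred term and treatment (SAP 2.9.3) and by study eye (SAP 5.3, Table 4.2.5), and protocol 9.4.8 adds a Fisher test for each term. By-subject slit-lamp data are in Data 4.2. A reader might infer that the trial could not distinguish chamber cells from redness at all. The documents do not support that; the limit is in Tables 6.1.1 and 6.1.2. The adverse event route still depends on the investigator recording the sign as an event.

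**The SAP may already provide the counts.** SAP 2.9 has a general rule of frequencies and percentages for categorical variables, and the table shells, which are not in the text available for review, might show grades. A general rule does not override the specific slit-lamp text, but the shells could settle the matter.

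**IOP.** The same protocol sentence covers IOP, for which SAP 5.5 says "Descriptive and inferential statistics of IOP will be presented by treatment". A reader might infer a second departure. Protocol 9.4.1, however, says "All continuous study assessments will be summarized by treatment and time point (as applicable) using descriptive statistics", and IOP is continuous. The conflict lies between two protocol sections.

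**External eye exam.** A reader might infer that its findings go unreported. It is paired with biomicroscopy in protocol 8.1, in the SAP 5.6 heading and in Data 4.2, and the text does not show whether findings outside the seven items are recorded. No finding can be built on this.

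**Heart rate and blood pressure.** It would be too strong to say that these data will not be reported. SAP 2.8 says "All existing data records including the repeat data records in the study database will be presented in data listings and CRF data tabulations", and protocol 9.4.1 and 9.7 contain general summary and listing commitments. What is missing is a specified table and listing.

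**Conclusion.** The mismatch for slit lamp is real: the protocol asks for discrete summaries of a graded primary endpoint, and the SAP text states continuous ones and an ANCOVA on the total. Under the wording of SAP 5.6, the two slit-lamp tables cannot separate worsening of one sign from another, as cases A and B show. Under the item-by-item reading of 2.9.3 the sign is named but the counts are still not stated. The illustration assumes integer grades that can rise by 2, and the conclusion is limited to the SAP text and table titles.

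The consequence is moderate. Adverse event tables and listings give another route to the same signs, and nothing here threatens the validity of the trial. The change should be made because the tables for a primary endpoint ought to show what the protocol says they will show. Counting subjects who worsen is a recommendation; 9.4.7 does not require it for slit lamp. The heart rate and blood pressure gap is a separate, minor omission.

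**What to change.** - **Slit lamp.** In SAP 2.9.3, SAP 5.6 and Tables 6.1.1 and 6.1.2, give for each of the seven items the number and percentage of subjects at each grade at each time point, by treatment and by study and fellow eye. Keep the total-score ANCOVA as supportive, and state what *individually* means.
- **Recommended addition.** Give the number and percentage of subjects worsening from pre-dose on each item. This goes beyond 9.4.7 for slit lamp and mirrors the visual acuity summary in SAP 5.4.
- **Heart rate and blood pressure.** Add one summary table and one named listing for the time points collected. Those time points are not visible, because protocol Table 1 is not in the text available for review, so change-from-pre-dose rows depend on what was measured.
- **IOP.** State in the SAP whether it follows protocol 9.4.1 or 9.4.7, since the two conflict.

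The cost is a few extra tables, one listing and some sentences in the SAP. No new data are needed. The wording should be settled before unmasking.
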